### 3 STUDY DESIGN

#### 3.1 Description of the Study

This is a Phase IV, open-label, multi-center study to evaluate the real world sustained virological response rate, subject adherence, and subject reported outcomes during and after treatment of non-cirrhotic genotype 1 chronic hepatitis C subjects aged 18 years and older, with the AbbVie 3 direct-acting antiviral (3-DAA) regimen of VIEKIRA PAK (ombitasvir, paritaprevir/r, dasabuvir), with or without ribavirin. Subjects may be treatment-naïve or treatment experienced with pegylated-interferon based regimens excluding regimens with direct-acting antiviral agents.

The study will be conducted at multiple KPSC Medical Centers and will screen approximately 275 subjects with an estimated 33% screen failure rate to enroll 200 subjects.

#### 3.2 Subject Population

Subjects will be considered treatment-naïve if they have never received any antiviral treatment for HCV infection.

Subjects will be considered treatment-experienced if they have received prior interferon-based therapy (including interferon or pegylated-interferon monotherapy; interferon and ribavirin; or pegylated-interferon and ribavirin). Treatment-experienced subjects with prior use of HCV DAA(s) are excluded from study participation.

Subjects with documentation available to classify prior response to interferon and ribavirin, or pegylated-interferon and ribavirin treatment will be categorized as one of the following:

- **Null-responder:** did not achieve a 1 log10 IU/mL reduction in HCV RNA by week 4 or a 2 log10 IU/mL reduction in HCV RNA by week 12 during a prior interferon and ribavirin, or pegylated-interferon and ribavirin treatment course
- **Partial-responder:** achieved at least a 2 log10 IU/mL reduction in HCV RNA by week 12 during a prior interferon and ribavirin or pegylated-interferon and ribavirin treatment course, but failed to achieve HCV RNA undetectable at the end of treatment
- **Relapser:** achieved undetectable HCV RNA at end of a prior interferon and ribavirin or pegylated-interferon and ribavirin treatment course, but HCV RNA was detectable following therapy completion

Subjects with a less well-characterized IFN-based treatment experience, including those subjects with incomplete HCV RNA and treatment date documentation, will be categorized as one of the following:

- **Relapse/breakthrough:** achieved at least one documented result of HCV RNA undetectable during a prior IFN and RBV ribavirin, or pegIFN and RBV treatment course
- **Non-responder:** did not achieve a documented result of HCV RNA undetectable or HCV RNA was detected at the end of treatment during a prior IFN and RBV, or pegIFN and RBV treatment course with insufficient data available to categorize as a breakthrough, partial or null responder
- **Interferon intolerant:** did not meet any of the above definitions of treatment-failure and discontinued IFN and RBV, or pegIFN and RBV therapy due to IFN intolerance
- **Interferon experienced-other:** Includes IFN, or pegIFN and RBV monotherapy; IFN and RBV, or pegIFN and RBV experienced subjects; Includes subjects who do not have adequate documentation of response. Subjects receiving interferon or peginterferon monotherapy must be categorized as 'Interferon experienced-other'.

### 3.3 Treatment Arms

Subjects who meet all eligibility criteria and provide written informed consent will be enrolled in the study and assigned to one of two treatment groups.

**Genotype 1a:** VIEKIRA PAK (ombitasvir, paritaprevir/r, dasabuvir) + RBV (ribavirin)

**Genotype 1b:** VIEKIRA PAK (ombitasvir, paritaprevir/r, dasabuvir)

See [Section 4.4](#) for more information.

### 3.4 Study Duration

#### Study Discontinuation

Southern California Permanente Medical Group (SCPMG) reserves the right to terminate this study at any time due to the incidence or severity of adverse events in this study that indicate a potential health hazard to subject or partner.

## 4 STUDY PRODUCT INFORMATION

For complete information on VIEKIRA PAK (ombitasvir, paritaprevir/r, dasabuvir), refer to the VIEKIRA PAK Package Insert version 12/2014. Select information from the document is available below.

For complete information on ribavirin, refer to the Ribavirin Package Insert version 08/2011. Select information from the document is available below.

### 4.1 Description

#### 4.1.1 VIEKIRA PAK (ombitasvir, paritaprevir/r, dasabuvir)

[figure not shown]
VIEKIRA PAK is ombitasvir, paritaprevir, ritonavir fixed dose combination tablets copackaged with dasabuvir tablets.

Ombitasvir, paritaprevir, ritonavir fixed dose combination tablet includes a hepatitis C virus NS5A inhibitor (ombitasvir), a hepatitis C virus NS3/4A protease inhibitor (paritaprevir), and a CYP3A inhibitor (ritonavir) that inhibits CYP3A mediated metabolism of paritaprevir, thereby providing increased plasma concentration of paritaprevir. Dasabuvir is a hepatitis C virus non-nucleoside NS5B palm polymerase inhibitor, which is supplied as separate tablets in the copackage. Both tablets are for oral administration.

[figure not shown]
### Ombitasvir

The chemical name of ombitasvir is Dimethyl [(2*S*,5*S*)-1-(4-*tert*-butylphenyl)pyrrolidine-2,5-diyl]bis {benzene-4,1-diylcarbamoyl(2*S*)pyrrolidine-2,1-diyl[(2*S*)-3-methyl-1-oxobutane-1,2-diyl]}biscarbamate hydrate. The molecular formula is C50H67N7O8•4.5H2O (hydrate) and the molecular weight for the drug substance is 975.20 (hydrate). The drug substance is white to light yellow to light pink powder, and is practically insoluble in aqueous buffers but is soluble in ethanol. Ombitasvir has the following molecular structure:

### Paritaprevir

The chemical name of paritaprevir is (2*R*,6*S*,12*Z*,13*aS*,14*aR*,16*aS*)-*N*-(cyclopropylsulfonyl)-6- {[[(5-methylpyrazin-2-yl)carbonyl]amino}-5,16-dioxo-2-(phenanthridin-6-yloxy)-1,2,3,6,7,8,9,10,11,13*a*,14,15,16,16*a*-tetradecahydrocyclopropa[*e*]pyrrolo[1,2-*a*][1,4]diazacyclopentadecine-14*a*(5*H*)-carboxamide dihydrate. The molecular formula is C40H43N7O7S•2H2O (dihydrate) and the molecular weight for the drug substance is 801.91 (dihydrate). The drug substance is white to off-white powder with very low water solubility. Paritaprevir has the following molecular structure:

[figure not shown]

### Ritonavir

The chemical name of ritonavir is [5*S*-(5*R*\*,8*R*\*,10*R*\*,11*R*\*)]10-Hydroxy-2-methyl-5-(1-methylethyl)-1-[2-(1-methylethyl)-4-thiazolyl]-3,6-dioxo-8,11-bis(phenylmethyl)-2,4,7,12-tetraazatridecan-13-oic acid,5-thiazolylmethyl ester. The molecular formula is C37H48N6O5S2

and the molecular weight for the drug substance is 720.95. The drug substance is white to off white to light tan powder practically insoluble in water and freely soluble in methanol and ethanol. Ritonavir has the following molecular structure:

[figure not shown]

#### Ombitasvir, Paritaprevir, Ritonavir Fixed-Dose Combination Tablets

Ombitasvir, paritaprevir, and ritonavir film-coated tablets are co-formulated immediate release tablets. The tablet contains copovidone, K value 28, vitamin E polyethylene glycol succinate, propylene glycol monolaurate Type I, sorbitan monolaurate, colloidal silicon dioxide/colloidal anhydrous silica, sodium stearyl fumarate, polyvinyl alcohol, polyethylene glycol 3350/macrogol 3350, talc, titanium dioxide, and iron oxide red. The strength for the tablet is 12.5 mg ombitasvir, 75 mg paritaprevir, 50 mg ritonavir.

#### Dasabuvir

The chemical name of dasabuvir is Sodium 3-(3-*tert*-butyl-4-methoxy-5-{6-[(methylsulfonyl)amino]naphthalene-2-yl}phenyl)-2,6-dioxo-3,6-dihydro-2H-pyrimidin-1-ide hydrate (1:1:1). The molecular formula is  $C_{26}H_{26}N_3O_5S \cdot Na \cdot H_2O$  (salt, hydrate) and the molecular weight of the drug substance is 533.57 (salt, hydrate). The drug substance is white to pale yellow to pink powder, slightly soluble in water and very slightly soluble in methanol and isopropyl alcohol. Dasabuvir has the following molecular structure:

[figure not shown]

Dasabuvir is formulated as a 250 mg film-coated, immediate release tablet containing microcrystalline cellulose (D50-100 um), microcrystalline cellulose (D50-50 um), lactose monohydrate, copovidone, croscarmellose sodium, colloidal silicon dioxide/anhydrous colloidal silica, magnesium stearate, polyvinyl alcohol, titanium dioxide, polyethylene glycol 3350/macrogol 3350, talc, and iron oxide yellow, iron oxide red and iron oxide black. Each tablet contains 270.3 mg dasabuvir sodium monohydrate equivalent to 250 mg dasabuvir.

#### **4.1.2 Ribavirin**

Ribavirin is a synthetic nucleoside analogue (purine analogue). The chemical name of ribavirin is 1-β-D-ribofuranosyl-1*H*-1,2,4-triazole-3-carboxamide and has the following structural formula:

Ribavirin is a white, crystalline powder. It is freely soluble in water and slightly soluble in anhydrous alcohol. The empirical formula is  $C_8H_{12}N_4O_5$  and the molecular weight is 244.21.

Ribavirin capsules USP consist of a white powder in a white, opaque, gelatin capsule. Each capsule, for oral administration, contains 200 mg ribavirin. In addition, each capsule contains the following inactive ingredients: corn starch, croscarmellose sodium, hypromellose, magnesium stearate, mannitol and povidone. The capsule shell consists of gelatin and titanium dioxide. The capsule is printed with edible blue pharmaceutical ink which is made of FD&C Blue #2 aluminum lake, propylene glycol, shellac and titanium dioxide.

## 4.2 Acquisition and Accountability

VIEKIRA PAK is manufactured by AbbVie Inc., North Chicago, IL 60064. Ribavirin is manufactured by Sandoz, Inc., Broomfield, CO 80020.

The investigational products are for investigational use only and are to be used only within the context of this study. The study drugs supplied for this study must be maintained under adequate security and stored under the conditions specified on the label until dispensed for subject use, returned to the Sponsor, or destroyed per local regulations.

## 4.3 Formulation, Packaging, Labeling, and Storage

### 4.3.1 VIEKIRA PAK

VIEKIRA PAK is dispensed in a monthly carton for a total of 28 days of therapy. Each monthly carton contains four weekly cartons. Each weekly carton contains seven daily dose packs. Each child resistant daily dose pack contains four tablets: two 12.5/75/50 mg ombitasvir, paritaprevir, ritonavir tablets and two 250 mg dasabuvir tablets, and indicates which tablets need to be taken in the morning and evening. The NDC number is NDC 0074-3093-28.

Ombitasvir, paritaprevir, ritonavir 12.5/75/50 mg tablets are pink-colored, film-coated, oblong biconvex shaped, debossed with “AV1” on one side. Dasabuvir 250 mg tablets are beige-colored, film-coated, oval-shaped, debossed with “AV2” on one side.

Store at or below 30°C (86°F).

### 4.3.2 Ribavirin

Ribavirin capsules USP, 200 mg are white, opaque, hard gelatin capsules imprinted (in blue) RIBAVIRIN over 200 mg on cap and GG 608 on body. Dispense in a tight container as defined in the USP. Store at 25°C (77°F); excursions permitted to 15° to 30°C (59° to 86°F)

#### 4.4 Dosage and Administration

Subjects who meet all eligibility criteria, and provide written informed consent will be enrolled in the study and assigned to either genotype 1a or genotype 1b treatment group and be administered the study drug as below:

Table 4. Treatment Regimen, Dosing and Duration per Arm

Treatment Arm	Treatment	Duration
Genotype 1a	VIEKIRA PAK + (RBV) ribavirin	12 weeks
	VIEKIRA PAK: 
 
Two ombitasvir, paritaprevir, ritonavir tablets once daily (in the morning) with a meal without regard to fat or calorie content) and
 
One dasabuvir tablet twice daily (morning and evening) with a meal without regard to fat or calorie content.
 
 RBV (ribavirin): Dosage is based on weight and adjusted for renal impairment subjects. 
 
If subject weighs less than or equal to 75 kg, 1000 mg daily in two divided doses with food.
 
If subject weighs greater than 75 kg, 1200 mg daily in two divided doses with food.
 
 Study drugs should be dosed together (e.g. VIEKIRA PAK with RBV in the morning with food, and dasabuvir with RBV in the evening with food).	
Genotype 1b	VIEKIRA PAK	12 weeks
	VIEKIRA PAK: 
 
Two ombitasvir, paritaprevir, ritonavir tablets once daily (in the morning) with a meal without regard to fat or calorie content) and
 
One dasabuvir tablet twice daily (morning and evening) with a meal without regard to fat or calorie content.
 
	

#### 4.5 Dose Modification

VIEKIRA PAK will not be dose-modified.

Ribavirin will be adjusted for renal impairment subjects. Ribavirin will be dose-modified for decreases in hemoglobin or decreased glomerular filtration rate as per the package insert or per the clinical judgment of the investigator.

#### 4.6 Toxicity and Safety Information

##### 4.6.1 VIEKIRA PAK

ALT Elevations: Discontinue ethinyl estradiol-containing medications prior to starting VIEKIRA PAK (alternative contraceptive methods are recommended).

In subjects receiving VIEKIRA PAK with ribavirin, the most commonly reported adverse reactions (greater than 10% of subjects) were fatigue, nausea, pruritus, other skin reactions, insomnia and asthenia. In subjects receiving VIEKIRA PAK without ribavirin, the most

commonly reported adverse reactions (greater than or equal to 5% of subjects) were nausea, pruritus and insomnia. Refer to the VIEKIRA PAK Package Insert for more information.

**4.6.2 Ribavirin**

The primary toxicity of ribavirin is hemolytic anemia. The anemia associated with ribavirin therapy may result in worsening of cardiac disease that has led to fatal and nonfatal myocardial infarctions. Patients with a history of significant or unstable cardiac disease should not be treated with ribavirin.

Significant teratogenic and embryocidal effects have been demonstrated in all animal species exposed to ribavirin. In addition, ribavirin has a multiple-dose half-life of 12 days, and so it may persist in nonplasma compartments for as long as 6 months. Therefore, ribavirin therapy is contraindicated in women, who are pregnant and in the male partners of women who are pregnant. Extreme care must be taken to avoid pregnancy during therapy and for 6 months after completion of treatment in both female patients and in female partners of male patients who are taking ribavirin therapy. At least two reliable forms of effective contraception must be utilized during treatment and during the 6-month post-treatment follow-up period. Refer to the Ribavirin Package Insert for more information.

**4.7 Prohibited Medication**

Estrogen-containing hormonal contraceptives, including oral, injectable, implantable, patch and ring varieties, may not be used during study drug treatment.

Participants must not receive contraindicated medication prior to study drug administration including, but not limited to those listed in Table 4, or medications contraindicated for ritonavir or ribavirin per FDA label. For those that receive ribavirin, contraindicated medications must be discontinued at least 2 weeks or 10 half-lives prior to study drug administration, whichever is longer.

Table 5. Medications Contraindicated for Use with Study Drug Regimen

Alfuzosin	Estrogen-containing	Phenytoin
Astemizole	Medications for Systemic Use	Pimozide
Carbamazepine	Fusidic Acid	Rifampin
Dihydroergotamine	Gemfibrozil	Sildenafil**
Efavirenz	Lovastatin	Simvastatin
Ergotamine	Methylergonovine	St. John's Wort
Ergonovine	Midazolam (oral)	Terfenadine
	Phenobarbital	Triazolam

\* Not all medications contraindicated with VIEKIRA PAK, ritonavir, and ribavirin are listed above. Refer to the most current package inserts or product labeling for each drug for a complete list of contraindicated medications.

\*\* When used for the treatment of pulmonary arterial hypertension

## 5 SELECTION OF SUBJECTS

### 5.1 Inclusion Criteria

To participate in this study the subject must **meet all** of the following inclusion criteria:

1. Male or female at least 18 years of age at time of screening.
2. Subject voluntarily signed the Informed Consent Form for the study.
3. Subject is able to adhere to study visit/ procedure schedule and protocol requirements
4. Subject, if female must not use estrogen-containing hormonal contraception including oral, injectable, implantable, patch and ring varieties during study drug treatment
5. Subject, if female must meet at least one of the following:
  - Subject of childbearing potential must agree to either
    - practice 2 effective contraceptive methods for study duration, starting Screening through 30 days after stopping study drug if not receiving ribavirin, 6 months/or as directed by ribavirin label if receiving ribavirin
    - practice total abstinence from sexual intercourse (minimum 1 complete menstrual cycle)
    - be sexually active with female partner only
  - Postmenopausal defined as age appropriate amenorrhea for  $\geq 2$  years prior to screening and post-menopausal state confirmed by follicle-stimulating hormone (FSH) level
  - Surgically sterile defined as bilateral tubal ligation or bilateral oophorectomy or hysterectomy
  - Has male sexual partner with vasectomy
6. Subject, if male, who is not surgically sterile and is sexually active with female partner of childbearing potential must agree to practice 2 effective contraceptive methods for study duration, starting at Screening through 30 days after stopping study drug if not receiving ribavirin, 7 months/or as directed by ribavirin label if receiving ribavirin
7. Subject must have at least one of the following indicators of chronic hepatitis C virus infection prior to study enrollment:
  - Positive anti-HCV antibody or HCV RNA  $> 10,000$  IU/mL at least 6 months before screening, and positive for HCV RNA at the time of screening
  - HCV RNA  $> 10,000$  IU/mL at screening and liver biopsy consistent with chronic HCV infection
  - Credible evidence of chronic hepatitis C as per the investigator and HCV RNA  $> 10,000$  IU/mL at the time of screening.
8. Subject has a screening laboratory result indicating HCV genotype 1-infection. Historical genotype within 6 months of screening may be used at the discretion of the investigator.

---

 Effective contraceptive methods outlined in informed consent form, subject information sheet, and other subject documents

 Effective contraceptive methods outlined in informed consent form, subject information sheet, and other subject documents

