### **6.2.3.3 Week 12 (Visit 6) - End of Treatment (EOT) Procedures**

The following assessments/procedures will be performed in-clinic:

- Pregnancy Test, Serum or Urine
- Obtain labs:
  - HCV RNA
  - CBC with differential
  - Creatinine
  - Liver panel (ALT, Alkaline Phosphatase, Total Bilirubin), AST and Direct Bilirubin
  - Additional labs as determined by the investigator
- Review concomitant medications
- Review for AEs
- Study drug accountability

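### Inclusion 5 can be met by a vasectomised partner alone, or by abstinence with no stated end, while Section 4.6.2 requires two contraceptive methods during ribavirin treatment and for 6 months after

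*Combined protocol and SAP*

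**What the plan says.** Inclusion 5 is a list of alternatives: "Subject, if female must meet at least one of the following". The item appears in both the Protocol Summary and Section 5.1, with the same routes.

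A woman of childbearing potential may agree to use two effective methods. In Section 5.1 that route is dated: "starting Screening through 30 days after stopping study drug if not receiving ribavirin, 6 months/or as directed by ribavirin label if receiving ribavirin". She may instead agree to "practice total abstinence from sexual intercourse (minimum 1 complete menstrual cycle"), or be sexually active with a female partner only. A separate bullet, at the same level as the postmenopausal and surgically sterile bullets, reads "Has male sexual partner with vasectomy".

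Section 4.6.2 covers ribavirin. Its instruction to avoid pregnancy applies "in both female patients and in female partners of male patients who are taking ribavirin therapy", and it continues: "At least two reliable forms of effective contraception must be utilized during treatment and during the 6-month post-treatment follow-up period". It describes teratogenic and embryocidal effects in every animal species exposed, and possible persistence of the drug for up to 6 months.

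Section 3.3 assigns every genotype 1a subject to "VIEKIRA PAK (ombitasvir, paritaprevir/r, dasabuvir) + RBV (ribavirin"). Genotype 1b subjects receive no ribavirin.

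**The concern.** The eligibility list and the ribavirin safety section give different requirements for the same women. Sites screen against the eligibility list. Two of its routes do not carry what Section 4.6.2 demands: one amounts to a single method, and the other has no stated end.

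What is at stake is subject safety with a drug that the protocol itself describes as teratogenic and that is mandatory in one arm. If the two sections differ, sites may apply different rules, and a subject may agree to less at entry than the protocol elsewhere says she must do. The point concerns only women receiving ribavirin, because Section 4.6.2 does not govern the ribavirin-free arm.

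**Working it through.** This is mainly a comparison of text. No sample-size, power or interval figure is involved.

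**1. Who is affected.** Women of childbearing potential in the genotype 1a arm (Section 3.3). Section 8.3.1 expects about 100 subjects per genotype group, presumably 80 to 120, counting both sexes. The documents do not say how many will be women of childbearing potential, or how many would use either route.

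**2. The two routes beside the two-method route and Section 4.6.2.**

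| Source | Methods | Start | End, with ribavirin |
|---|---|---|---|
| Inclusion 5, two-method route | Two | Screening | 6 months (Section 5.1) or 7 months (Summary), or per label |
| Inclusion 5, abstinence route | Abstinence | Not stated | Not stated; lower bound of one cycle |
| Inclusion 5, vasectomised-partner route | One | Not stated | Not stated |
| Section 4.6.2 | At least two | Treatment | 6 months after treatment |

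**3. Vasectomy route.** It counts as one method against at least two, with no ribavirin condition. A woman who qualifies this way can still conceive. Section 6.1.7 recognises this: it exempts documented tubal ligation, oophorectomy, hysterectomy and confirmed menopause from pregnancy testing, but not a partner's vasectomy. The requirement in Section 4.6.2 therefore applies to her, and inclusion 5 does not ask her to meet it.

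**4. Abstinence route.** Abstinence kept up throughout would serve the purpose of Section 4.6.2. The mismatch is that the route directly above it has a start and an end, while this one has only a lower bound not linked to study drug.

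**5. The period that needs to be stated.** Treatment ends at the visit headed "Week 12 (Visit 6) - End of Treatment (EOT) Procedures". Taking a month as 365/12 days:

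- Treatment: 12 × 7 = 84 days.
- With 6 months after: 84 + 183 = about 267 days.
- With 7 months after: 84 + 213 = about 297 days.

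The last study visit is at post-treatment week 12, day 84 after the last dose. The 6-month period then has 183 − 84 = 99 days (about 14 weeks) still to run, and the 7-month period 213 − 84 = 129 days (about 18 weeks).

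**6. The post-ribavirin periods also disagree.** For women it is 6 months in Sections 4.6.2 and 5.1 item 5, but 7 months in Summary item 5. For men, item 6 gives 7 months in both places, while Section 4.6.2 gives 6 months for their female partners. Section 6.1.7 recommends monthly pregnancy testing for at least 7 months. Dating the two open routes means settling this as well.

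**The case against.** The strongest reply is that Section 4.6.2 is not meant to override the eligibility list. Section 4 is introduced as selected package-insert information, and Section 4.6.2 sits under toxicity and safety information. Read with no exceptions at all, it would also conflict with the postmenopausal, surgically sterile and female-partner-only routes, which nobody would call an error. Item 6 likewise exempts surgically sterile men from two methods, so accepting vasectomy looks deliberate.

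Much of this stands. Section 4.6.2 is evidently aimed at women who could conceive through intercourse, and vasectomy was probably accepted on purpose. But its sentence is worded as a requirement, and a woman with a vasectomised partner is within its evident scope. If the route is an intended exception, or if Section 4.6.2 is only background, the protocol should say so.

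A second reply is that the one-cycle phrase is a run-in before treatment. It may be, but the text does not say so, and the end would still be unstated.

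A third is that safeguards exist. Women on both routes have scheduled pregnancy tests from screening to post-treatment week 12 (Appendix A), are counselled at the last visit and are advised to test monthly afterwards (Section 6.1.7). This is correct and limits the consequence. Tests detect a pregnancy; they do not replace contraception, and after week 12 they are only recommended.

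A fourth is that footnote 1 to Section 5.1 refers to the consent form and subject documents for the contraceptive methods. Those were not available for this review and may help subjects. They would not remove a contradiction within the protocol.

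**Conclusion.** Wrong as written: an internal contradiction in an operative eligibility rule. A genotype 1a woman of childbearing potential can satisfy inclusion 5 in both places without meeting Section 4.6.2. The conflict is plain for the vasectomy route; for abstinence it is limited to the missing start and end. The number of women affected is unknown and may be small. The conclusion rests on the protocol text alone and on reading Section 4.6.2 as binding.

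Three stronger readings are tempting, and the documents do not support them.

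- A reader might infer that abstinence may stop after one cycle, and might express that cycle as a fraction of the required period. The wording sets a minimum, not an end date, so such a fraction measures nothing that the protocol permits.
- A reader might infer that sites have no text to hold subjects to. They have Section 4.6.2 itself, and inclusion 3 requires ability to adhere to protocol requirements.
- A reader might infer damage to the SVR12 result, because Section 6.3.4 stops ribavirin on a positive pregnancy test. No frequency is given, so an effect on SVR12 is speculative. Neither the sample size nor the SVR12 analysis rests on this point.

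**What to change.** Reconcile inclusion 5, in the Protocol Summary and Section 5.1, with Section 4.6.2. The revised text should say, for subjects receiving ribavirin, whether the vasectomised-partner and abstinence routes are accepted, and what period each covers from start to end. If Section 4.6.2 is intended to allow exceptions, it should name them. The sponsor decides the rule; this review does not say which is right.

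Reconcile the 6- and 7-month periods in the Summary, Sections 4.6.2, 5.1 (items 5 and 6) and 6.1.7 in the same amendment, since any end date given to these routes depends on them. Check the consent form and subject documents against the result.

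The cost is amendment and consent wording, with no new visits or tests, and possibly a longer stated commitment for a few subjects.
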